Patients who discontinue study medication for any reason (e.g., disease progression, an adverse event [AE], etc.) other than withdrawal of consent will continue to be followed for survival and new anti-cancer therapy every 3 months after last dose until death, for a minimum of 12 months after the last patient has been enrolled or until all patients have died, withdrawn consent or are lost to follow-up (whichever occurs first).

END OF STUDY

The end of study will occur when all patients have been followed for survival for a minimum period of 12 months after the last patient has been enrolled or until all patients have died, withdrawn consent or are lost to follow up, whichever occurs first.

At this time, the trial will end and no further data will be collected on the clinical database for this study. The end of the MO28072 study is defined as the last patient last visit at the end of the follow-up period.

Prior to the closure of the trial, the Sponsor may offer patients who have completed the protocol-mandated minimum 12-month safety follow-up and who continue to benefit from vemurafenib therapy, the opportunity to receive continued vemurafenib via enrolment in the GO28399 extension trial. Should the study be closed due to Sponsor decision, the Sponsor will offer all patients still receiving vemurafenib therapy the opportunity to receive continued treatment with vemurafenib via enrollment in the GO28399 extension trial at the time of study closure.

INVESTIGATIONAL MEDICAL PRODUCT(S): DOSE/ ROUTE/ REGIMEN

Patients will receive:

- Cohorts 1 to 7 (except the Cohort 3b): continuous oral doses of vemurafenib 960 mg b.i.d. starting on Day 1 of the study Treatment Phase until the development of progressive disease (as per Investigator assessment), unacceptable toxicity, consent withdrawal, protocol violation endangering patient's safety, death, reasons deemed critical by the treating physician or study termination by the Sponsor.
- Cohort 3b. cetuximab intravenous (IV) weekly (see [Appendix 1](#) for body surface area calculation) starting on Day 1 of the study Treatment Phase and continuous oral doses of vemurafenib b.i.d. starting on Day 2 of the study Treatment Phase

until the development of progressive disease (as per Investigator assessment), unacceptable toxicity, consent withdrawal, protocol violation endangering patient's safety, death, reasons deemed critical by the treating physician or study termination by the Sponsor.

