Patients with ECD/LCH have the option of discontinuing vemurafenib treatment after one year, if the investigator considers it to be in the best interest of the patient. Patients can then resume vemurafenib treatment if they become symptomatic or if their scans show worsening of their disease.

For Part 1 of Cohort 3b, the dose escalation levels of vemurafenib and cetuximab combination will be as follows:

Dose Level	Vemurafenib	Cetuximab
1	720 mg b.i.d. starting on Day 2 of cycle 1	Cetuximab: 300 mg/m ² loading dose on Day 1 of Treatment Phase, then 200 mg/m ² weekly
2	720 mg b.i.d. starting on Day 2 of cycle 1	Cetuximab: 400 mg/m ² loading dose on Day 1 of Treatment Phase, then 250 mg/m ² weekly
3	960 mg b.i.d. starting on Day 2 of cycle 1	Cetuximab: 400 mg/m ² loading dose on Day 1 of Treatment Phase, then 250 mg/m ² weekly

If the dose levels above are not tolerated then the following provisional dose levels may be considered as alternative to any of the above dose levels after discussion between the Sponsor and study Steering Committee (see [Section 6.3.1](#)).

Dose Level	Vemurafenib	Cetuximab
1A	720 mg b.i.d. starting on Day 2 of cycle 1	Cetuximab: 200 mg/m ² loading dose on Day 1 of Treatment Phase, then 125 mg/m ² weekly
2A	720 mg b.i.d. starting on Day 2 of cycle 1	Cetuximab: 300 mg/m ² loading dose on Day 1 of Treatment Phase, then 250 mg/m ² weekly
3A	960 mg b.i.d. starting on Day 2 of cycle 1	Cetuximab: 300 mg/m ² loading dose on Day 1 of Treatment Phase, then 250 mg/m ² weekly

Patients included in Part 2 of Cohort 3b of the study will receive vemurafenib and cetuximab at the doses recommended during the dose escalation part.

If recruitment is expanded in any cohort (due to promising efficacy seen in Stage II), patients who are part of this expansion will receive the same treatment as patients who were treated in Stage II of that cohort.

Patients who develop disease progression but, in the opinion of the Investigator, would still benefit from continuing study treatment may continue treatment with study treatment after discussion with the Sponsor.

NON-INVESTIGATIONAL MEDICAL PRODUCT(S)

N/A

COMPARATOR “DRUG” (OR STANDARD OF CARE): DOSE/ ROUTE/ REGIMEN

N/A

CENTRES

This is a multinational, multicentre study with approximately 30 centres.

EFFICACY

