4.4 CONCOMITANT THERAPY

At study initiation, patients should continue with their concomitant medications, as directed by their physician, with the exception of study precluded medications (see below and [Section 4.3](#) above). All concomitant medication must be fully recorded on the eCRF. Additionally, any diagnostic, therapeutic, or surgical procedure performed during the study period should be recorded including the date, indication, description of the procedure(s) and any clinical findings.

Due to the underlying illness and the frequency of co-existent medical conditions in this patient population, all concomitant medication or treatment required by the patient will be at the discretion of the treating physician. In general, concomitant medications and therapies deemed necessary for the supportive care and safety of the patient are allowed, provided their use is documented in the patient records and on the eCRF.

For Cohort 3b only, prior to the first infusion of cetuximab, patients must receive premedication with an antihistamine and a corticosteroid. This premedication is recommended prior to all subsequent infusions. See cetuximab SPC for further details (79).

See [Appendix 9](#) for more details for prostate cancer patients.

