18. Performed by the treating physician as part of the evaluation for SCC. Should be done at Safety Follow-up Visit at 28 days (± 5 days) and at 6 months following study drug discontinuation or prior to the initiation of another anti-neoplastic therapy (whichever occurs first).
19. CT of the chest for the evaluation of non-cutaneous SCC. The routinely scheduled radiographic assessment for tumour burden may be used (if available) as the chest CT for the evaluation of non-cutaneous SCC while the patient is taking study medication.
20. For patients in Part I of Cohort 3b, vemurafenib will start on Day 2 of Cycle 1 (administered while in hospital).
21. Patients will keep a diary to record ONLY those occasions when a vemurafenib dose was missed (morning or evening, each day of treatment). The patient will bring this diary with him/her to each study visit to allow missed doses to be recorded by the Investigator.
22. Only for patients enrolled in the Part 1 of Cohort 3b (the dose-escalation part of the study)
23. All concomitant medications during the study started within 14 days prior to the screening visit and up to the Safety Follow-up Visit must be recorded.
24. During screening AEs are not recorded in the eCRF unless they are SAEs which are related to protocol-mandated procedures. ALL AEs (including SAEs) must be recorded from the time of first study drug administration. After the last dose of study medication any new AEs should be reported up to 28 days after last dose. The Investigator is not required to actively monitor patients for adverse events after the end of the adverse event reporting period (defined as 28 days after the last dose of study drug). However the Sponsor should be notified if the Investigator becomes aware of any SAE that occurs after the end of the adverse event reporting period, if the event is believed to be related to prior study drug treatment. After the study site has closed, the Investigator should report adverse reactions as mandated in the protocol directly to the Local Drug Safety Affiliate.

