6.2 DOSE AND SCHEDULE OF VEMURAFENIB

Patients will receive continuous oral doses of vemurafenib 960 mg b.i.d. without scheduled dose interruption starting on Day 1 (except for Part I of Cohort 3b where vemurafenib starts on Day 2 [administered while in hospital], see [Section 6.3](#)) of the Treatment Period until the development of progressive disease, unacceptable toxicity, consent withdrawal, protocol violation endangering the patient's safety, death, reasons deemed by the Investigator, or study termination by the Sponsor.

Vemurafenib is supplied in 240 mg film-coated tablets packed in bottles for oral administration. Patients should be instructed to take four tablets in the morning and four tablets approximately 12 hours later in the evening (total daily dose of 1920 mg [960 mg b.i.d.]) (except for Cohort 3b where vemurafenib dose will be determined by the dose finding phase, see [Section 6.3](#)). Each dose should always be taken in the same manner i.e. either with or without a meal.

If vomiting occurs during the course of treatment, no re-dosing of the patient is allowed before the next scheduled dose. However if a patient forgets to take a dose, it can be taken up to 4 hours prior to the next dose.

If a patient misses a dose (e.g., due to emesis), he or she should be instructed not to take or make up that dose and to resume dosing with the next scheduled dose. Missed doses will not be made up. Patients will be instructed to bring all unused tablets to each study visit for assessment of compliance.

Patients who develop disease progression but, in the opinion of the Investigator, would still benefit from continuing study treatment may continue treatment with study treatment after discussion with the Sponsor.

Patients will be given a dosing exception diary to record the time and date of *missed* study medication doses. Any such data provided by the patient will be transcribed from the diary to the eCRF by the study coordinators.

A 6-week supply of study medication (three 120-tablet bottles) will be given to the patient on Day 1 of the first cycle. From Cycle 2 onwards a 4-week supply of study medication (two 120-tablet bottles) will be given to the patient on Day 1 of each dosing cycle. Patients will be instructed not to open a new bottle until the previous bottle has been finished and to bring their study medication and bottles (used or unused) back to the clinic at the next study visit for reconciliation.

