6.3.2.2 Dose-limiting toxicities (Cohort 3b only)

DLT is defined as a clinically significant adverse event or abnormal laboratory value assessed as unrelated to disease progression, undercurrent illness, or concomitant medications and occurring during the first 4 weeks of treatment with the combination of vemurafenib and cetuximab.

For the purposes of this protocol, the following adverse events determined to be possibly, probably or definitely related to the combination of cetuximab and vemurafenib that occur during the 28 days following the first administration of the combination of vemurafenib and cetuximab at any dose level and that meet any of the following criteria are considered to be dose-limiting toxicities (DLT) that count for the determination of the MTD.

Toxicity grades are defined in the NCI CTCAE v 4.0 ([80](#)).

- Grade ≥ 3 non-haematological toxicity (other than untreated nausea, vomiting and diarrhoea and excluding alopecia)
- Grade ≥ 3 nausea, vomiting or diarrhoea refractory to appropriate treatment for at least 2 days
- Grade 4 anaemia lasting > 7 consecutive days
- Neutropenia Grade 4 lasting > 7 consecutive days
- Neutropenia Grade 3 or 4 complicated by fever and/or infection (ANC $<1.0 \times 10^9/L$; fever $\geq 38.5^\circ C$)
- Grade 4 thrombocytopenia lasting > 7 consecutive days
- Treatment delay >33% of the scheduled doses over 28 days due to treatment related toxicity

Skin and subcutaneous tissue toxicity is not considered a DLT unless a dose reduction of study treatment is required to permit continuous dosing.

6.3.3 Dose Modifications, Interruptions, and Delays for Vemurafenib and Cetuximab (Cohort 3b only)

For all patients in Cohort 3b when an occurring toxicity can be clearly ascribed to either cetuximab or vemurafenib, it will be considered to only dose reduce the compound responsible for the toxicity. See [Table 13](#) for the recommended cetuximab dose interruptions/ modifications and [Section 6.2.1](#) for vemurafenib dose reductions.

When an occurring toxicity cannot be clearly ascribed to either cetuximab or vemurafenib, both drugs will be dose reduced as per guidance in [Table 11](#) and [Table 13](#) for vemurafenib and cetuximab respectively.

Table 13:
Dose Interruption/Modification Criteria for Cetuximab

Toxicity Grade (CTCAE, v4.0) ^a	Cetuximab dose changes during current treatment period	Dose adjustments for resumption of treatment of weekly dose

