8.3.3 Safety Data Analysis

The safety variables will be summarized for the safety population where the safety population is SP1 to SP7. All safety variables will be summarized for each cohort.

All AEs will be assessed according to the NCI CTCAE, v4.0, grading system. The analysis of AEs will focus on treatment-emergent AEs, i.e., AEs occurring on the day of or after first administration of study drug (vemurafenib). Non-treatment emergent AEs (i.e., those occurring before commencement of study medication) will only be listed.

The incidence, type, and severity of AEs will be summarized according to the primary system-organ class (SOC) and within each SOC, by MedDRA preferred term. Summary tables may be presented for time to first onset of the AE of special interest.

AEs leading to treatment interruption and discontinuation and SAEs will be analysed in a similar way to all AEs. Cause of death will also be summarized and listed.

Results from skin evaluation, head and neck evaluations, chest CT scan (e.g., number of lesions, SCC - keratoacanthoma type, etc.) will be summarized using frequencies and percentages. The number of patients prematurely discontinued from the treatment with corresponding reason for discontinuation will be summarized and listed. The discontinuation from study will be also summarized and listed.

Descriptive statistics will be presented for cumulative vemurafenib doses and duration of exposure.

Laboratory parameters, haematology, and serum biochemistry will be presented in shift tables of NCI-CTCAE grade at baseline versus worst grade during the Treatment Period. The summary of laboratory parameters presented by means, standard deviation, minimum, and maximum will be also presented.

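### In Cohort 3b Part 1 the treatment-emergent AE definition starts at the first vemurafenib dose (Day 2), so AEs after the Day 1 cetuximab infusion fit neither AE class as written

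*Protocol*

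**What the plan says.** Section 8.3.3 centres the AE analysis on treatment-emergent events, defined as "AEs occurring on the day of or after first administration of study drug (vemurafenib" given in brackets as the drug meant. The synopsis (Safety Data Analysis) has the same rule. Neither place makes an exception for Cohort 3b.

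The next sentence in Section 8.3.3 covers non-treatment-emergent AEs: "those occurring before commencement of study medication) will only be listed". SAEs and AEs leading to interruption or discontinuation are to be handled in the same manner as AEs overall.

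The Cohort 3b dosing order is:

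- **Cetuximab.** The synopsis dose-level table for Part 1 gives a "loading dose on Day 1 of Treatment Phase", and Table 8b also shows cetuximab on Day 1.
- **Vemurafenib, Part 1.** Table 8b, footnote 20: "For patients in Part I of Cohort 3b, vemurafenib will start on Day 2 of Cycle 1 (administered while in hospital". Section 6.2 agrees: "except for Part I of Cohort 3b where vemurafenib starts on Day 2".
- **Vemurafenib, Cohort 3b as a whole.** The synopsis (Investigational Medical Product(s)) says "continuous oral doses of vemurafenib b.i.d. starting on Day 2 of the study Treatment Phase", without restricting this to Part 1.

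Table 8b, footnote 24 starts AE recording at the first dose of study drug. Section 8.2 puts in the safety population anyone who received at least one dose of study medication.

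**The concern.** The definition suits the monotherapy cohorts, where vemurafenib is the only study drug and its first dose is the start of treatment. Cohort 3b Part 1 has a second study drug that is given first. A reaction to it on Day 1 happens on treatment but before the treatment-emergent window opens.

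The protocol treats infusion reactions as a foreseen risk. Section 4.4 requires that "prior to the first infusion of cetuximab, patients must receive premedication with an antihistamine and a corticosteroid", and Section 6.3.3 has rules for infusion reactions, including permanent discontinuation of cetuximab for serious ones. Safety and tolerability of the combination is a stated Cohort 3b objective (Section 2.2), and AEs are a primary safety variable (Section 8.1.3). What is at stake is whether the published Cohort 3b tables show what happened on the first infusion day.

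**Working it through.** No sample size, power or error rate is involved. The check is to place a Day 1 event against each rule.

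**Step 1. Dates in Cohort 3b Part 1.** First cetuximab: Day 1 (synopsis dose table, Table 8b). First vemurafenib: Day 2 (Table 8b footnote 20, Section 6.2).

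**Step 2. Is an AE with onset on Day 1 after the infusion treatment-emergent?** The window opens on the day of first vemurafenib, Day 2. Day 1 is earlier than Day 2, so the answer is no. Counting the whole day of first dosing does not help, because the two first doses fall on different days.

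**Step 3. Is it in the listed-only class?** That class needs onset before study medication begins.

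- If cetuximab counts as study medication, the event comes after the start, so it is not in this class. It then belongs to neither class.
- If cetuximab did not count, the event would be listed and not summarised.

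The first reading fits the protocol better. Section 6.9 names both agents as study drugs. Section 3.1 makes Day 1 the first day study medication is received. The notes to Table 8b equate Day 1 with the first dose of study drug, whereas those to Table 8a name vemurafenib. On either reading the event misses the treatment-emergent summaries.

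**Step 4. Is it collected, and is the patient counted?** Yes to both. For Cohort 3b, Table 8b footnote 24 records AEs from the first study drug; the corresponding Table 8a footnote 30 says first vemurafenib. The collection rule was therefore adapted for this cohort and the analysis rule was not. Under Section 8.2 one cetuximab dose is enough to enter the safety population. A patient who reacts on Day 1 and never takes vemurafenib is in the denominator but has no vemurafenib date from which an AE could be treatment-emergent.

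**Step 5. Size.** Section 8.4 caps the dose-finding part at 18 patients, so the firm extent is up to 18 patients for one calendar day each. For Part 2 the passages disagree. The synopsis gives Day 2 for all of Cohort 3b, Section 6.2 confines Day 2 to Part 1, and Table 8b marks Part 2 vemurafenib dispensing on Day 1. If Part 2 starts on Day 1, its Day 1 events are captured. If it starts on Day 2, the extent rises to 18 + 19 = 37, the maximum Section 8.4 gives for this cohort.

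**Step 6. Does the DLT summary close the gap?** Not clearly. Section 6.3.2.2 uses the "28 days following the first administration of the combination of vemurafenib and cetuximab at any dose level". The escalation guidelines in Section 6.3.2 count 28 days from the first administration of vemurafenib and cetuximab. Neither says whether a day with cetuximab alone is inside the window. DLT checks on Days 8, 15, 22 and 29 (Section 5.3.8) look as if they are counted from Day 1, but that does not settle it. The DLT summary would in any case show only events that qualify as DLTs.

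**The case against.** The strongest reply is that the protocol never states an exclusion. The only sentence that sends events to listings is tied to the start of study medication, and a Day 1 event does not meet it. Section 8.3.3 says the analysis concentrates on treatment-emergent AEs and then promises a summary of AEs in general. On this view there are two badly matched sentences and a sensible programmer would include Day 1. This stands in part: it is right to say that the summaries can omit these events, not that they must. But the stated definition, applied as written, leaves them out.

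A reader might infer four stronger things, none of which the protocol supports:

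- **That toxicity is understated when the dose is chosen.** Section 6.3.2 rests escalation on a review of all available safety data, and the recommended dose on the MTD and an overall safety assessment. Neither depends on the treatment-emergent flag. Day 1 events are recorded, and SAEs go to the sponsor within 24 hours (Section 7.3.4).
- **That infusion reactions cluster at the first infusion, so most would be lost.** The protocol gives no distribution of their timing. Premedication is mandatory before the first infusion and recommended before later ones, which is not a frequency. Once vemurafenib has started, reactions to later infusions fall inside the window.
- **That all 37 patients are affected.** This depends on the unresolved Part 2 start day.
- **That DLTs on Day 1 are missed.** The window wording is unclear on this; it does not exclude Day 1.

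**Conclusion.** The point holds as a rule that is stated wrongly for one cohort. It is not a detail left to the SAP, because the protocol fixes the anchor and names the drug. In Cohort 3b Part 1 an AE on Day 1 after cetuximab does not meet the treatment-emergent definition and, with cetuximab counted as study medication, does not meet the listed-only definition either. The AE, SAE and discontinuation summaries can therefore omit such reactions, although they are collected and the patient is in the denominator.

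The firm extent is one day in up to 18 patients. It widens to at most 37 before any cohort expansion, and only if Part 2 also starts vemurafenib on Day 2. The damage is to the completeness of the reported Cohort 3b safety tables. How many events would be lost cannot be derived from the protocol, and no effect on dose selection is shown.

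**What to change.** In Section 8.3.3 and in the synopsis, define treatment-emergent AEs as those with onset on or after the day of first administration of any study medication (vemurafenib or cetuximab). Use the same anchor in the sentence on non-treatment-emergent AEs, so that every AE falls into exactly one class.

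Two reconciliations go with this:

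- The synopsis, Section 6.2 and Table 8b must agree on the day vemurafenib starts in Cohort 3b Part 2.
- The DLT-window wordings in the Section 6.3.2 escalation guidelines and Section 6.3.2.2 must agree, so that it is clear whether Day 1 counts. No particular window or schedule is proposed here.

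The cost of the definition change is a few words in two places and one anchor date in the programming. No new data are needed, since Cohort 3b AEs are already recorded from the first study drug. The monotherapy cohorts do not change, because vemurafenib is their only study drug.

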8.3.4 Interim Analysis

The study will be analysed for efficacy at Stage I and Stage II and the dose escalation for Part 1 of Cohort 3b ([Section 6.3.2.1](#)), at week 16 and at 9 months (see primary analysis, [Section 8.3.2](#)) for expanded cohorts. All cohorts will be analysed at the end of the study.

In case a cohort/indication is expanded up to 70 patients, the primary analysis for efficacy will occur once all patients have been followed up for 9 months after last patient had been enrolled in that cohort, or the patient develops progressive disease, withdraws consent, or is lost to follow-up, whichever occurs first.

